An analysis to assess the efficacy of dupilumab if patients adhere to the treatment as directed is also specified. In this approach, the severe exacerbation events reported after the premature treatment discontinuation will be excluded from the analysis. Any exacerbation obtained after the first permanent stepping-up of background asthma medication (following at least two severe exacerbation per protocol) will also be excluded from the analysis. The supportive analysis for the primary endpoint will be performed in the Type 2 inflammatory asthma phenotype and baseline blood eosinophils ≥ 0.3 Giga/L populations. A negative binomial model with the same set of covariates as specified for the primary endpoint analysis in each of the Type 2 inflammatory asthma phenotype and baseline blood eosinophils ≥ 0.3 Giga/L populations will be used. This model will include severe exacerbation events occurring during the treatment epoch before any permanent treatment regimen change (including permanent IMP discontinuation and/or step-up of controller medication) as the response variable and the log transformed duration of the treatment epoch or from randomization to first permanent treatment regimen change whichever is shorter will be the offset variable. This approach defines the estimand to be the efficacy of dupilumab with treatment adherence.

Handling of missing data

If patients withdraw from the study before Visit 28 (Week 52), severe exacerbation events that may occur after study discontinuation will not be observed. These patients are considered as patients with missing data for the severe exacerbation endpoint. Number of patients with missing data, reasons and timing for patient withdrawals will be summarized by treatment groups. Summary statistics of selected demographic and baseline disease characteristics will be provided for patients with missing data and patients with complete data separately. Graphical summaries of the dropout patterns such as Kaplan-Meier plots of time to study discontinuation with different reasons of discontinuation may be provided to examine if there is any different missing pattern between treatment groups. In addition, the following sensitivity analyses will be conducted to assess the robustness of the conclusion drawn based on the main model for the primary analysis to the missing data:

- *Pattern mixture model (PMM-MI with logistic regression model)*

For each patient with partial missing data of severe exacerbation events, the unobserved number of events after study discontinuation up to Week 52 will be imputed on monthly basis. Since the definition of severe exacerbation in [Section 2.1.3.1](#) requires the start dates of 2 consecutive severe exacerbation events experienced by one patient to depart at least 28 days from each other, each patient is possible to have a maximum of one event per month that is defined as 28 days. A logistic regression model therefore can be used to impute whether a patient has an event or not for each of the corresponding unobservable months. This imputation will be repeated multiple times. A final statistical inference will be obtained by using Rubins' formula to combine the binomial regression results based on each of the imputed datasets. Details of the PMM model are described in [Appendix D](#).

- *Control-based PMM*

Similar to aforementioned PMM model except that the individual monthly mean probability will be calculated based on observations in placebo arm only in the logistic regression, with adjustment of missing observation duration.

- *Tipping point analysis*

Similar to aforementioned PMM model except that if a patient with missing data is on dupilumab, the odds in the logistic model for each unobservable month will be increased, and vice versa if the patient is on placebo, the odds will be decreased. This adjustment will artificially lower the predicted event rates in placebo group and increase the predicted event rates in Dupilumab group. For each increasing/decreasing ratio, a p-value can be obtained based on the imputed dataset with this specific ratio. A sequence of different ratios will be explored until p-value becomes >0.05 .

The missing data sensitivity analyses for the primary endpoint analysis will be performed in the Type 2 inflammatory asthma phenotype and baseline blood eosinophils ≥ 0.3 Giga/L populations. For each of the above methods, a negative binomial model will be fitted using the complete dataset composed of observed and imputed data, including the total number of observed and imputed events during the 52 weeks as the response variable. When performing the sensitivity analyses in the population with Type 2 inflammatory asthma phenotype, the model will include the treatment group, age, baseline weight (≤ 30 kg, >30 kg), region (pooled country), baseline eosinophil level, baseline FeNO level, baseline ICS dose level and number of severe exacerbation events within 1 year prior to the study as covariates. When performing the sensitivity analyses in the population with baseline blood eosinophils ≥ 0.3 Giga/L, the baseline eosinophil level will be removed from the model covariates. Log transformed observation duration will be the offset variable.

More details of the imputation and analyses methods are provided in [Appendix D](#).

Sensitivity analysis related to COVID-19 Pandemic

To assess missing data due to COVID-19 pandemic, missing data from patients who were discontinued from the study before Week 52 due to COVID-19 will be imputed using a manner similar to pattern mixture model as mentioned above except breaking down the 'Other' discontinuation reason into 'Due to COVID-19 or not' when defining the missing patterns.

Subgroup analyses

To assess the consistency of treatment effects across the subgroup levels, subgroup analyses will be performed for the annualized rate of severe exacerbation event during the 52-week treatment period by:

- Gender (Male, Female)
- Region (Latin America, Eastern Europe, and Western Countries)
- Race (Caucasian/White, Black/of African descent, Asian/Oriental, all the other)
- Background ICS dose levels at randomization (medium, high)

- Baseline blood eosinophil level (<0.3 Giga/L, ≥ 0.3 Giga/L; <0.15 Giga/L, ≥ 0.15 Giga/L; <0.15 Giga/L, ≥ 0.15 - <0.3 Giga/L, ≥ 0.3 - <0.5 cells/ μ L, ≥ 0.5 cells/ μ L)
- Baseline FeNO level (<20 ppb, ≥ 20 - <35 ppb, ≥ 35 ppb)
- Eos-FeNO Quadrant (0.15-20) 1 (H-H): Baseline blood eosinophil level ≥ 0.15 Giga/L and Baseline FeNO ≥ 20 ppb
- Eos-FeNO Quadrant (0.15-20) 2 (H-L): Baseline blood eosinophil level ≥ 0.15 Giga/L and Baseline FeNO <20 ppb
- Eos-FeNO Quadrant (0.15-20) 3 (L-H): Baseline blood eosinophil level <0.15 Giga/L and Baseline FeNO ≥ 20 ppb
- Eos-FeNO Quadrant (0.15-20) 4 (L-L): Baseline blood eosinophil level <0.15 Giga/L and Baseline FeNO <20 ppb
- Eos-FeNO Quadrant (0.3-20) 1 (H-H): Baseline blood eosinophil level ≥ 0.3 Giga/L and Baseline FeNO ≥ 20 ppb
- Eos-FeNO Quadrant (0.3-20) 2 (H-L): Baseline blood eosinophil level ≥ 0.3 Giga/L and Baseline FeNO <20 ppb
- Eos-FeNO Quadrant (0.3-20) 3 (L-H): Baseline blood eosinophil level <0.3 Giga/L and Baseline FeNO ≥ 20 ppb
- Eos-FeNO Quadrant (0.3-20) 4 (L-L): Baseline blood eosinophil level <0.3 Giga/L and Baseline FeNO <20 ppb
- Background controller type at randomization (ICS only, ICS + LABA)
- Baseline predicted FEV1% ($<80\%$, $\geq 80\%$)
- Baseline predicted FEV1% ($<$ median, \geq median)
- Baseline ACQ-7-IA (≤ 2 , >2)
- Baseline weight (≤ 30 , >30 kg)
- Atopic medical condition (Yes, No)
- Baseline Total IgE ($<$ median, \geq median)
- Baseline Total IgE (<100 IU/mL, ≥ 100 IU/mL)
- Age at onset of asthma (0 - <2 , 2 - <6 , ≥ 6)
- Number of severe asthma exacerbation prior to the study as defined in [Section 2.1.1](#) (≤ 1 , $=2$, >2)

Additional EOS-FeNO Quadrant analysis will be performed using alternative cut-off value for the baseline FeNO:

- Eos-FeNO Quadrant (0.15-35) 1 (H-H): Baseline blood eosinophil level ≥ 0.15 Giga/L and Baseline FeNO ≥ 35 ppb
- Eos-FeNO Quadrant (0.15-35) 2 (H-L): Baseline blood eosinophil level ≥ 0.15 Giga/L and Baseline FeNO <35 ppb

- Eos-FeNO Quadrant (0.15-35) 3 (L-H): Baseline blood eosinophil level <0.15 Giga/L and Baseline FeNO \geq 35 ppb
- Eos-FeNO Quadrant (0.15-35) 4 (L-L): Baseline blood eosinophil level <0.15 Giga/L and Baseline FeNO <35 ppb

A patient is considered to have ongoing atopic medical condition if he/she has any of the following: atopic dermatitis, allergic conjunctivitis or rhinitis, eosinophilic esophagitis, food allergy, hives; or has baseline serum total IgE \geq 100 IU/mL and at least one positive aeroantigen specific IgE (\geq 0.35 IU/mL) at baseline.

The aforementioned subgroup analyses (except for the baseline eosinophil levels and baseline FeNO levels) will be performed in the Type 2 inflammatory asthma phenotype population and baseline blood eosinophils \geq 0.3 Giga/L population; and, the subgroup analyses concerning the baseline blood eosinophil level and baseline FeNO level will be performed in the full ITT population. The annualized rate of severe exacerbation events as defined in [Section 2.1.3.1](#) will be analyzed using a negative binomial regression model.

When performing the subgroup analysis in the Type 2 inflammatory asthma phenotype population or the full ITT population, the model will include the total number of events that occur during the observation period defined above as the response variable, with the treatment arm, age, baseline weight (\leq 30kg, >30kg), region, baseline blood eosinophil level (<0.3 Giga/L, \geq 0.3 Giga/L), baseline FeNO level (<20 ppb, \geq 20 ppb), baseline ICS dose level (medium/high) and number of severe exacerbation events within 1 year prior to the study as covariates. When performing the subgroup analysis in the baseline blood eosinophils \geq 0.3 Giga/L population, the baseline eosinophil level will be removed from the model covariates. Furthermore, in the Type 2 inflammatory asthma phenotype, baseline blood eosinophils \geq 0.3 Giga/L, or full ITT population, when performing the subgroup analysis that is defined by age, baseline weight, region, baseline blood eosinophil level, baseline FeNO level, baseline ICS dose level, or number of severe exacerbation events within 1 year prior to the study, the covariate that defines the subgroup will be removed from the model covariates.

[figure not shown]
Treatment groups, baseline weight, region, baseline eosinophil level, baseline FeNO level, and baseline ICS dose level will be treated as categorical variables. Age and number of severe exacerbation events within 1 year prior to the study will be treated as continuous variables. Log transformed observation duration will be the offset variable. In the case where the negative binomial regression model may not converge, a categorical variable for the number of severe exacerbation events within 1 year prior to study (1, 2, more than 2) will replace the corresponding continuous variable in the model.

Treatment by subgroup interaction and its p-value will be derived from a negative binomial model. This model will include the total number of events occurring during the observation period as the response variable, with the treatment groups, age, baseline weight, region, baseline eosinophil level, baseline FeNO level, baseline ICS dose level, number of severe exacerbation events within 1 year prior to the study, subgroup (if different than the aforementioned covariates) and treatment by subgroup interaction as covariates. Log transformed observation duration will be

the offset variable. If quantitative treatment by subgroup interaction is detected with nominal p-value <0.05 for any subgroup factor, the Gail-Simon test will be performed to evaluate possible qualitative interaction. Summary statistics of severe exacerbations will be provided within each subgroup. Forest plot of relative risks and corresponding CIs and forest plot of risk differences and corresponding CIs comparing dupilumab vs. placebo for the subgroups will be provided.

Treatment-by-Type 2 biomarker interaction

To examine the ability of FeNO to predict the treatment effect of dupilumab independent of blood eosinophil levels for the primary endpoint, treatment-by-biomarker interactions will be tested using negative binomial regression models that include the total number of severe exacerbation events during 52-week treatment period as the response variable, and with the following different sets of model covariates, respectively. A threshold value of 0.15 will be utilized for the nominal p value of interaction test.

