1.3 DETERMINATION OF SAMPLE SIZE

The sample size of this study was based on a comparison between dupilumab versus placebo with regard to the primary endpoint of annualized rate of severe exacerbations over 52 weeks of treatment for the 3 populations of interest: patients with baseline blood eosinophils ≥ 0.3 Giga/L, patients with baseline blood eosinophils ≥ 0.15 Giga/L, and Type 2 inflammatory asthma phenotype populations (as defined in [Section 2.3.1](#)), with assuming the number of severe exacerbations follows a negative binomial distribution and a randomization ratio of 2:1.

The sample size calculation assumes a linear discontinuation rate (20% at 1 year), thus the average exposure duration for patients is 0.9 year. The assumed relative risk reductions are based on the results in the Phase 3 asthma study EFC13579 (QUEST).

[figure not shown]
To achieve target sample size for each of the populations stated above, at least a total of 402 patients in the overall population (268 for dupilumab and 134 for placebo) need to be randomized assuming approximately 86% of the randomized patients have the Type 2

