2.4.4.1 Analysis of primary efficacy endpoint(s)

Primary statistical model and adjustment for covariates

The primary analysis of the annualized rate of severe exacerbation events during the 52-week placebo-controlled treatment period is to assess the efficacy of dupilumab. In this primary approach, for the patients who prematurely discontinue treatment, their off-treatment measurements up to Week 52 or the study withdrawal whichever comes earlier will be included for the analysis. Patients who permanently discontinue the study medication will be asked and encouraged to return to the clinic for all remaining study visits. If a patient stays in study until the end of the 52-week treatment period, all severe exacerbation events that happen up to Visit 28 will be included in the primary analysis, regardless whether the patient is on-treatment or not, and the observation duration is defined as from randomization to Visit 28. If a patient withdraws from the study prior to the end of the 52-week treatment period, all observed severe exacerbation events up to the last contact date will be included in the analysis, and the observation duration is defined as from randomization to the last contact date. No imputation will be performed for the unobserved events that may happen after study discontinuation and up to Week 52. This estimand compares

the rate of severe exacerbation for the patients randomized to the dupilumab and placebo arms, regardless of what treatment patients actually received. It assesses the benefits of the treatment policy or strategy relative to placebo.

The annualized rate of severe exacerbation events as defined in [Section 2.1.3.1](#) will be analyzed using a negative binomial regression model. The analysis for the annualized severe exacerbation rate will be performed in the Type 2 inflammatory asthma phenotype, baseline blood eosinophils ≥ 0.3 Giga/L, baseline blood eosinophils ≥ 0.15 Giga/L, baseline FeNO ≥ 20 ppb and full ITT populations.

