class outcome trt01pn weight eosbgp1n cntygr1 icsgrp fenoblgrn ;  
monotone reg (asmanum/details)  
logistic (outcome=trt01pn age weight eosbgp1n cntygr1 icsgrp fenoblgrn asmanum/details  
DESCENDING);  
var eosbgp1n cntygr1 age icsgrp trt01pn fenoblgrn asmanum outcome;  
run;
```

Step 4. A negative binomial model with the same set of covariates as in the primary endpoint analysis will be fitted with 40 sets of complete datasets obtained in Step 3, so as to obtain 40 sets of treatment effect estimates and p-values accordingly. Log transformed observation duration will be the offset variable for patients who complete the 52-Week treatment/study period, and log transformed 52 weeks will be the offset variable for patients who discontinue the study before Visit 18 (Week 52). At last, the SAS MIANALYZE procedure will be used to generate statistical inferences by combining results from the 40 analyses using Rubin's formula.

Step 4 can be realized by using PROC MIANALYZE in SAS. Sample code can be found below

```
proc mianalyze data=rr_conv;  
by Label;  
modeleffects Estimate;  
stderr StdErr;  
ods output ParameterEstimates=rr_pooled;  
run;  
proc mianalyze data=aer_conv;  
by TRT01PN;  
modeleffects Estimate;  
stderr;  
ods output ParameterEstimates=aer_pooled;  
run;
```

- **Control-based PMM**

All steps are the same as the aforementioned approach except in **Step 2**: the individual monthly mean probability will be calculated based on observations in placebo arm only, with adjustment of missing observation duration.

- **Tipping point analysis**

The tipping point analysis for severe exacerbation events will use the similar approach as PMM-MI with tipping values for the odds

Step 1. Estimation for the monthly binary event probability using observed data

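### The SAP states two incompatible offsets for the primary endpoint's missing-data sensitivity analyses, and the sound one carries a wrong visit number

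*SAP*

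**What the plan says.** SAP section 2.4.4.1, under its missing-data heading, describes the model to be fitted after imputation for all three methods. The model is a negative binomial regression, "including the total number of observed and imputed events during the 52 weeks as the response variable". The same paragraph ends: "Log transformed observation duration will be the offset variable". Earlier in that section, for a child who leaves the study early, "the observation duration is defined as from randomization to the last contact date". The next sentence after the offset reads "More details of the imputation and analyses methods are provided in" Appendix D.

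Appendix D, Step 4, splits the offset by completion status. For completers: "Log transformed observation duration will be the offset variable for patients who complete the 52-Week treatment/study period". For the rest: "log transformed 52 weeks will be the offset variable for patients who discontinue the study before Visit 18 (Week 52"). This text appears under the pattern mixture model and again under the tipping point analysis. The control-based version inherits it: "All steps are the same as the aforementioned approach except in" Step 2.

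In the protocol's study flow chart (section 1.2) and in the SAP's visit-window tables (section 2.5.4), Visit 18 is Week 32 and Visit 28 is Week 52. SAP section 2.4.4.1 itself pairs Visit 28 with Week 52 when it defines who has missing data.

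**The concern.** In a count model the offset must cover the same time as the count. After imputation, a withdrawn child's count covers 52 weeks. If the offset stops at last contact, the numerator spans a year and the denominator a fraction of one. A child who leaves at Week 4 with one imputed event would enter at 1/(4/52) = 13 events per year.

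These analyses exist to show whether the primary result survives missing data. With a mismatched offset they could strengthen or weaken that result for a reason unrelated to the missing-data assumption under test. The tipping point search stops when the p-value passes 0.05, so the offset also affects where it tips. A pre-specified plan should not leave the programmer to choose between two rules.

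**Working it through.** **Inputs.** Withdrawal d = 20% at one year, linear, with average exposure 0.9 year (SAP section 1.3: "The sample size calculation assumes a linear discontinuation rate (20% at 1 year), thus the average exposure duration for patients is 0.9 year"). All other withdrawal percentages below are assumptions.

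**1. The plan's own figure.** Completers contribute 1 year and withdrawals half a year on average: 0.80 × 1 + 0.20 × 0.5 = 0.90 year. This reproduces the SAP.

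**2. Crude rate under each offset.** The numerator E (observed plus imputed events) is the same under both rules.
- Appendix D offset: E / (N × 1)
- Section 2.4.4.1 offset: E / (N × (1 − d/2))
- Ratio: 1 / (1 − d/2)

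| Withdrawal d | Overstatement factor |
|---|---|
| 2% | 1.010 |
| 5% | 1.026 |
| 10% | 1.053 |
| 20% (planning value) | 1.111 |
| 30% | 1.176 |

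**3. Crude rate ratio, dupilumab over placebo.** It is multiplied by (1 − d_placebo/2) / (1 − d_dupilumab/2).
- Equal withdrawal: factor 1
- 25% placebo, 15% dupilumab: 0.875/0.925 = 0.946
- 15% placebo, 25% dupilumab: 0.925/0.875 = 1.057

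**4. Negative binomial fit (illustration only).** Current planning rates and dispersion are blacked out. The simulations therefore used the superseded values in SAP Table 1: placebo rate 1.0, rate ratio 0.5, dispersion 1.5. At 20% withdrawal in both arms the section 2.4.4.1 offset inflated the fitted rates by about 16 to 20%. This exceeds the crude 11% because early withdrawals get very high individual rates.

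| Withdrawal, placebo / dupilumab | Rate ratio, Appendix D offset | Rate ratio, 2.4.4.1 offset |
|---|---|---|
| 25% / 15% | 0.487 | 0.432 |
| 15% / 25% | 0.501 | 0.531 |

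Analysing observed events over observed time gave 0.486 and 0.498 in the same two scenarios, so the Appendix D offset showed no material bias.

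**5. The visit number.** Followed literally, Visit 18 (Week 32) leaves withdrawals between Weeks 32 and 52 in neither offset group.
- Share affected at 20% linear withdrawal: 20/52 × 20% = 7.7%
- Mean unobserved time in that group: 10 weeks
- Time lost if they are given observed duration: 0.077 × 10/52 = 0.0148 year per child
- Crude factor: 1/(1 − 0.0148) = 1.015

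A simulated fit put the effect at about 2%.

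**The case against.** The strongest reply is that the right rule is already written. Section 2.4.4.1 points to Appendix D directly after its offset sentence, and Step 4 there is specific and correct. A specific rule normally governs a one-line summary. The definition that ends at last contact also belongs to the primary analysis, where nothing is imputed. Carrying it into the imputed dataset is an inference. The visit label is plainly a slip, since the same phrase says Week 52 and Step 3 of Appendix D imputes through Month 13, labelled Week 52.

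Most of this stands. It makes Appendix D the probable intention and the Week 52 reading the natural one. It does not remove the contradiction. The 2.4.4.1 sentence closes the very paragraph that specifies these models, makes no exception for withdrawals, and offers Appendix D as further detail rather than as an override. Appendix D itself treats observation duration and 52 weeks as different quantities, so the summary cannot be read as shorthand for the detailed rule. The COVID-19 analysis is modelled on the pattern mixture method but has no entry of its own in Appendix D, so it is open to the same ambiguity.

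A reader might go further and infer that the planned sensitivity analyses overstate rates by at least 11% and bias the rate ratio. The documents do not support that. Under Appendix D the time at risk matches the count. Nor is 11% a floor: it is the value at a discontinuation rate used for sample size. Imputation applies only to children who leave the study, and those who stop treatment are encouraged to stay in follow-up.

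**Conclusion.** The SAP contains a real contradiction: two stated offset rules for one set of analyses, one of which gives a wrong answer. If the 2.4.4.1 rule were programmed, crude rates would be about 11% too high at 20% linear withdrawal and about 5% too high at 10%. The rate ratio would shift in a direction set by which arm loses more children. Under Appendix D, read as Week 52, there is no such bias. The visit-number slip alone is worth about 2% on rates.

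The crude figures rest on linear withdrawal. The fitted figures also rest on superseded planning values, assumed withdrawal imbalances and a simpler imputation than the SAP's monthly logistic model, so they show direction and rough scale only. The primary analysis imputes nothing and is unaffected.

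**What to change.** - In SAP section 2.4.4.1, replace the offset sentence in the missing-data sensitivity paragraph with: for patients who withdraw from the study before Visit 28 (Week 52), whose events are imputed to Week 52, the offset is log(52 weeks); for patients who complete the 52 weeks, it is log observation duration. Say that the COVID-19 analysis uses the same rule.
- In Appendix D, Step 4, change Visit 18 to Visit 28 under both the pattern mixture model and the tipping point analysis.

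The cost is a few wording edits, with no new data and no added analysis. They should be made before unblinding, so that the offset is not chosen with results in view.

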Appendix D Handling of missing data

Annualized severe exacerbation events during the 52-Week period

- ***Pattern mixture model (PMM)***

Step 1. The 52-week observation period is partitioned into monthly (4-week) segments. In the analysis, for each patient, in each month, an imputation flag (impute_{fl}) will indicate whether the patient needs imputation in that month.

Step 2. *Calculation of observed monthly mean of event count*

Within each month, the logistic regression model will be fitted to the observed data to model coefficient estimates and the estimated variance-covariance matrix, with adjusting for the planned treatment group, age, baseline weight (≤ 30 kg, > 30 kg), region (pooled country), baseline eosinophil level (removed for the baseline eosinophils ≥ 0.3 Giga/L population), baseline FeNO level, baseline ICS dose level, and number of severe exacerbation events within 1 year prior to the study. From the posterior distribution of the model coefficients, we randomly draw 40 sets of iid samples. As a result, for each patient and in each month, 40 estimated probabilities can be obtained by using the 40 samples of coefficients and the patient's covariates values.

Step 3. *Imputation of event count after study withdrawal*

If a patient withdraws from the study at the k th ($1 \leq k < 28$) day of Month i prior to Week 52, and experienced a severe exacerbation within the first k days, this patient will be considered as “observed” (impute_{fl}=0) up to Month i and will need imputations (impute_{fl}=1) from Month $i+1$ to Month 13 (Week 52).

If a patient withdraws from the study at the k th ($1 \leq k < 28$) day of Month i prior to Week 52, and has no severe exacerbation in Month i , this patient will be considered as “observed” (impute_{fl}=0) up to Month $i-1$ and will need imputations (impute_{fl}=1) from Month i to Month 13 (Week 52).

For a patient who needs imputation from Month $i+1$ to Month 13, in each month, 40 independent random samples will be respectively drawn from 40 estimated Bernoulli distributions, whose probabilities are obtained in Step 2. For each patient who early withdraws from the study, 40 sets of complete event count data can be obtained by summing the observed event count prior to withdrawal and each series of imputed binary events after withdrawal up to Week 52.

Step 2 and 3 can be realized by using PROC MI in SAS. Sample code can be found below:

```
proc mi data=dd seed=9816388 nimpute=40 out=outdata;  
by month;  

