Step 4. A negative binomial model with the same set of covariates as in the primary analysis will be fitted to the 40 sets of complete datasets obtained in Step 3, so as to obtain 40 sets of treatment effect estimates and p-values accordingly. Log transformed observation duration will be the offset variable for patients who complete the 52-Week treatment/study period, and log transformed 52 weeks will be the offset variable for patients who discontinue the study before Visit 18 (Week 52). Then, the SAS MIANALYZE procedure will be used to generate statistical inferences by combining results from the 40 analyses using Rubin's formula.

Step 2, 3 and 4 will be repeated iteratively until the p-value for combined treatment effect of dupilumab compared to placebo estimated in Step 4 is >0.05 .

Change from baseline in % predicted pre-BD FEV1 at Week 12

Pattern mixture model-multiple imputation (PMM-MI)

Step 1. Monotone missing pattern was induced by Markov Chain Monte Carlo (MCMC) method using PROC MI: for patients who have missing values at intermediate visits, but have value at subsequent visits, the intermediate missing values were imputed assuming a multivariate normal distribution over observations from all visits. 40 datasets with a monotone missing pattern will be obtained using this method.

Step2. For each of the imputed dataset with monotone missing pattern obtained in Step 1, the remaining missing data will be imputed using the regression method for the monotone pattern with adjustment for covariates including response variable, treatment groups, baseline weight ($\leq 30\text{kg}$, $>30\text{kg}$), region (pooled country), ethnicity, baseline eosinophil level (removed for the baseline eosinophils ≥ 0.3 Giga/L population), baseline FeNO level, baseline ICS dose level, and baseline % predicted pre-BD FEV1 and missing pattern defined by reason of treatment discontinuation. All available data in the monotone missing pattern data will be used. 40 fully imputed datasets are obtained.

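### The COVID-19 sensitivity analysis for the primary endpoint splits a discontinuation-reason pattern that the exacerbation imputation model does not contain, so its agreement with the standard imputation would not show robustness to pandemic withdrawals

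*SAP*

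**What the plan says.** SAP 2.4.4.1 (sensitivity analysis related to the COVID-19 pandemic) concerns children who left the study before Week 52 because of COVID-19. It states that their missing data "will be imputed using a manner similar to pattern mixture model as mentioned above except breaking down the" 'Other' reason. The one stated change from that model is thus "breaking down the 'Other' discontinuation reason into 'Due to COVID-19 or not' when defining the missing patterns".

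The model it points back to is the monthly imputation for severe exacerbations in the same section: "A logistic regression model therefore can be used to impute whether a patient has an event or not" in each unobserved 28-day month. Appendix D gives the detail. Step 2 adjusts for planned treatment, age, weight, region, eosinophil level, "baseline FeNO level, baseline ICS dose level, and number of severe exacerbation events within 1 year prior to the study". The sample code runs PROC MI by month with 40 imputations and the statement "logistic (outcome=trt01pn age weight eosbgp1n cntygr1 icsgrp fenoblgrn asmanum/details".

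A pattern based on reason appears elsewhere, in the Week 12 FEV1 imputation. There Appendix D (PMM-MI, Step 2) adjusts for "missing pattern defined by reason of treatment discontinuation", and SAP 2.4.4.2.1 lists the same reason among the imputation covariates.

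**The concern.** The COVID-19 analysis is defined entirely by a change to a component that its parent model lacks. If the programmer follows Appendix D, a child who left because of the pandemic and a child who left for any other reason, with the same covariates, get the same imputation distribution. Nothing specific to COVID-19 is assumed, so nothing specific to COVID-19 is tested.

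SAP Table 2 says the COVID-19 analyses were added to evaluate the effect of the pandemic on study conduct. This is the only COVID-specific missing-data analysis that the SAP defines for the primary endpoint. If its result sits beside the PMM result and the two agree, a reader could take that as reassurance about pandemic withdrawals, although the agreement is built in.

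**Working it through.** The plan states no figure for this analysis, so there is none to reproduce. The check is of model content, followed by an illustration.

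**1. Where a reason for discontinuation enters**

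| Place in SAP | Endpoint | Reason or pattern term? |
|---|---|---|
| 2.4.4.1, COVID-19 paragraph | Exacerbations | Presupposes an 'Other' category to split |
| 2.4.4.1, PMM | Exacerbations | None |
| Appendix D, PMM Step 2 | Exacerbations | None; eight covariates listed |
| Appendix D, PROC MI code | Exacerbations | None in the LOGISTIC or VAR statement; BY month only |
| 2.4.4.2.1 and Appendix D, PMM-MI Step 2 | Week 12 FEV1 | Yes, reason for stopping treatment |
| 2.2 and 2.4.4.1, handling of missing data | Disposition, dropout | Descriptive summaries only |

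**2. What follows for the draws**

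For child i in month m the model is logit(p_im) = x_i'β_m, where x_i holds the eight Appendix D covariates. The COVID-19 label R_i is not in x_i, so the distribution of the imputed event given x_i is the same for R_i = COVID-19 and R_i = not. Two readings remain:

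- All withdrawers are imputed. This is the same model on the same data, so the result equals the PMM apart from Monte Carlo error if the seed changes.
- Only COVID-19 withdrawers are imputed, and other withdrawers keep their observed count and observed-time offset. The numbers change, but the COVID-19 draws are still the PMM's missing-at-random draws.

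**3. Illustration**

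The assumptions are:

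- 345 children (the approximate type 2 population in SAP 1.1), 2:1
- rates 1.0 and 0.5, dispersion 1.5 (from the superseded sample-size text)
- withdrawal probability 20%, about half of it due to COVID-19
- three generic covariates in place of those listed
- withdrawal placed at month boundaries
- 40 imputations, negative binomial analysis, Rubin's rules

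One simulated data set had 61 withdrawals, 33 of them due to COVID-19.

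| Analysis | Rate ratio | SE (log) |
|---|---|---|
| PMM | 0.565 | 0.199 |
| 'Other' split, Appendix D covariates, all imputed | 0.565 | 0.199 |
| Only COVID-19 withdrawals imputed | 0.556 | 0.200 |

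The first two rows agree by construction, because the label is not in the model. The third differs by ln(0.565/0.556) = 0.016 on the log scale, and 0.016/0.199 = 0.08 of a standard error.

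**4. Could a study-withdrawal reason be added to the monthly model?**

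The 52 weeks are 13 months of 28 days (13 × 28 = 364). Under Appendix D Step 3, a child who withdraws during Month i counts as observed in Month i only if an exacerbation occurred in it. Otherwise observation ends at Month i−1. For Month 13:

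- withdrew in Month 12 or earlier: unobserved
- withdrew in Month 13 without an event: unobserved
- withdrew in Month 13 with an event: observed, outcome 1

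The observed Month 13 outcomes of COVID-19 withdrawers are therefore either absent or all 1. Their coefficient is inestimable in the first case and perfectly separated in the second, however many such children there are. Earlier months thin out progressively. In the illustration the COVID-19 withdrawers still observed numbered 33 in Month 1, 12 in Month 9, 4 in Month 12 and 0 in Month 13. They had no events in Months 10 to 13, while 23 to 33 of them needed imputation.

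**The case against.** The SAP says the manner is similar to the PMM, not identical, and it mentions defining patterns. That may signal an intention to add reason patterns that Appendix D does not show. This stands as a reading. The analysis is then unspecified: there are no categories, no model term, no rule for sparse cells, and no choice between reason for stopping treatment and reason for leaving the study.

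A pattern by reason for stopping treatment, as in the FEV1 model, could have outcome data after discontinuation, because children who stop treatment are encouraged to stay and their off-treatment events count. The Month 13 argument does not defeat that version. But the COVID-19 paragraph concerns children who left the study, and the SAP defines no such pattern for exacerbations.

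A reader might infer that the analysis must return the PMM estimate exactly and carries no information at all. The documents do not support that. The sentence can be read as imputing COVID-19 withdrawals only, which changes the numbers slightly, and the count and timing of those withdrawals are not given.

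It is also fair to say that the proposed replacement still imputes COVID-19 withdrawals as missing at random. What it adds is a contrast: only the treatment of COVID-19 withdrawals separates it from the all-control-based result. The current plan has no such comparison.

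**Conclusion.** The point holds for this one supportive analysis. As written, it applies no COVID-specific assumption to COVID-19 withdrawals. Its result will equal the PMM or differ slightly from it (0.08 of a standard error in the illustration), and agreement is not evidence of robustness to pandemic withdrawals. This rests on Appendix D being followed as printed. The size of the slight difference depends on assumed inputs; the absence of a reason term and the Month 13 result do not.

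A reader might go on to infer that the primary result is unprotected against missing data. The documents do not support that. The control-based PMM and the tipping-point analysis cover all withdrawers, including those due to COVID-19, and stress departures from missing at random. Numbers, reasons and timing of withdrawal are summarised by arm. No step of the testing hierarchy in SAP 2.4.4.4 depends on the COVID-19 analysis.

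**What to change.** Replace the COVID-19 rule in SAP 2.4.4.1 and add it to Appendix D:

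- Impute study withdrawals before Week 52 due to COVID-19 with the existing PMM (missing at random, both arms in the model).
- Impute all other study withdrawals with the existing control-based rule.
- Analyse with the same negative binomial model and combine with Rubin's rules.
- Report beside the PMM and the all-control-based result. The difference from the all-control-based result shows how much the assumption about COVID-19 withdrawals matters.

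State that the classifying variable is the reason for leaving the study, and fix the COVID-19 classification before unblinding. SAP 2.2 already tabulates withdrawals before Week 52 by main reason, and the present COVID-19 paragraph already presumes that these children can be identified.

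The cost is SAP wording and one extra supportive run that combines two imputations already planned. The primary test and the testing hierarchy do not change.
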